10.1 Confidentiality	page 19
10.2 Modifications of the protocol	page 19
10.3 Participant Reimbursement	page 19
10.4 Financial Disclosure and Conflicts of Interest	page 19
11. USE OF DATA AND PUBLICATIONS POLICY	page 20
12. ETHICAL CONSIDERATIONS.....	page 20-21
13. APPENDIX.....	pages 22-28
13.1 Trial Inclusion Form.....	pages 22-23
13.2 References.....	pages 23-28

PROTOCOL SYNOPSIS

Title: *The broader health effects associated with newborn Hepatitis B vaccination: An investigator-initiated randomized controlled trial in Guinea-Bissau*

Objective: To determine whether a single dose of monovalent Hepatitis B (HBV0) provided at birth or up to age 1 week (<8 days) is associated with severe morbidity in the first 6 weeks of life (before other vaccines are administered), and with atopic dermatitis (AD) by 2 years of age and neurodevelopment by 5 years of age, when compared with no vaccine (control). Both randomization groups will receive the recommended neonatal BCG and OPV vaccines, co-administered with HBV0 in the intervention group.

GLOSSARY OF ABBREVIATIONS

ABBREVIATION TERM

aOR, Adjusted Odds Ratio

aRR, Adjusted Risk Ratio

BCG, Bacille Calmette-Guérin

BHP, Bandim Health Project

CI, Confidence interval

Co-PI, Co-Principal Investigator

DSMB, Data and Safety Monitoring Board

HepB, Hepatitis B vaccine in infancy (part of the pentavalent vaccine)

HBsAg, Hepatitis B surface antigen

HBV0, Hepatitis B vaccine, at birth dose

HDSS, Health and Demographic Surveillance System

HNSM, Hospital Nacional Simão Mendes

HR, Hazard Ratio

NSEs, non-specific effects (of vaccines)

PI, Principal Investigator

PS, Procurement Services (UNICEF)

OPV0, Oral Polio Vaccine, at birth dose

RCT, Randomized Controlled Trial

RDT, Rapid Diagnostic Test

SDU, University of Southern Denmark

1.2.3 Independent Data and Safety Monitoring Board

An independent Data and Safety Monitoring Committee (DSMB) will be established by the study group prior to the initiation of the trial. The DSMB's Terms of Reference will be established at the inception of the trial, outlining the Board's purpose, composition, responsibilities, and operational procedures. The DSMB will consist of a minimum of three senior clinicians or researchers, including at least one statistician. Trial progress will be monitored through 6-monthly blinded progress reports submitted to the DSMB by the trial team. The DSMB will review any major proposed modifications to the trial (such as termination, or an increase in sample size) and provide advice to the PI and team. The DSMB will convene face-to-face or by conference call before the start of the trial, after half the proposed number of newborns have been enrolled and followed-up, and again after three-quarters have been enrolled – or as determined by the DSMB. The DSMB will review the trial design, informed consent process, data collection forms, safety measures, the statistical analysis plan, and visit the trial site once during the conduct of the trial.

1.3 Sponsor

The Sponsor of the trial is the University of Southern Denmark.

1.4 Funding and Resources

External funding to finance the trial is necessary to fund the activities and has been granted. By December 2025, financial support for conducting the trial has been awarded from Pershing Square Foundation, Bluebell Foundation, and the US CDC.

The external funders have no role in the planning, conduct, or reporting of the trial.

2. INTRODUCTION AND BACKGROUND

2.1 Background Information

WHO recommends three vaccines at birth in low-income settings: Bacille Calmette Guérin (BCG) vaccine against tuberculosis, oral polio vaccine (OPV0) and hepatitis B vaccine. While much is known about the overall health benefits of BCG and OPV at birth, less is known about hepatitis B vaccine. The present study therefore focusses on investigating the overall health effects of hepatitis B vaccine at birth (HBV0).

Non-specific effects of vaccines. At the Bandim Health Project (BHP), a long-standing research collaboration between Guinea-Bissau's Ministry of Health and the University of Southern Denmark (SDU), 48 years of population data has uncovered that vaccines can have **non-specific effects (NSEs)**, also at times referred to as *off-target, heterologous, pathogen-agnostic or secondary vaccine*

effects), i.e. beneficial or detrimental effects not explained by the specific protection against the targeted disease.[12,13] NSEs are at least partially mediated by induction of *trained immunity* resulting in a modified innate immune response to subsequent unrelated infections.[12,14]

A meta-analysis of three randomized controlled trials (RCTs) in Guinea-Bissau reported that administration of BCG-Denmark given soon after birth reduced neonatal mortality in low-birth-weight newborns by 38% (95% CI 17% to 54%) with infections and most notably neonatal sepsis accounting for the excess deaths among controls.[1,2] In addition, there tended to be fewer hospital admissions with sepsis by 6 weeks of age among neonates randomized to BCG at birth.[2] The beneficial effect of BCG-Denmark lasted until a different vaccine was given at 6 weeks of age. The first dose of OPV0 has been shown to further reduce mortality when given with BCG during the first two days of life, the mortality reduction comparing BCG+OPV vs BCG alone being 42% (10%-62%).[15] This effect was especially evident for males and OPV was especially efficacious against fatal respiratory infections.[16] The findings regarding BCG led to national vaccine policy changes in Guinea-Bissau and inspired related research globally.[4,17–24] In a recent cluster-RCT from Guinea-Bissau, providing BCG + OPV0 at home visits within 72 hours of birth was associated with a 59% (8%-82%) reduction in early infant mortality, when compared with home visits without provision of vaccines.[23] A recent RCT from India in babies weighing below 2,000 g reproduced the finding of significantly fewer cases of fatal neonatal sepsis and reduced all-cause mortality risk when BCG + OPV was provided shortly after birth, compared with vaccination at discharge.[24]

Hepatitis B. Hepatitis B virus is a major global health concern, not least in sub-Saharan Africa, where it is a leading cause of chronic hepatitis, cirrhosis and fatal liver cancer.[25–27] Infection acquired perinatally from mother to child (vertical transmission) or during early childhood (horizontal transmission) carries an elevated risk of chronic infection and severe disease downstream.[27]

Hepatitis B vaccination. Hepatitis B vaccination at birth (**HBV0**) is the most effective approach to prevent vertical transmission[27] and pentavalent vaccines provided at 6, 10, and 14 weeks of age provide protection against horizontal hepatitis B transmission.[28]

A systematic Cochrane review of RCTs has shown that HBV0 reduces vertical transmission by 72% (60%-80%), but noted limited data on adverse events.[29] The use of HBV0 is especially important in countries with a high prevalence of hepatitis B surface antigen (**HBsAg**), yet WHO recommends universal HBV0 (including in neonates with a birth weight <2,000g and premature neonates), also in high-income countries.[27] While Australia, New Zealand and Japan have a universal HBV0 policy, most European countries only provide targeted HBV0 to babies born to HBsAg-positive mothers.[30] In the US, the policy was recently updated so that HBV0 is no longer recommended to newborns born to a mother that tested negative for HBsAg.[31] Only 15 of 47 countries in the WHO Africa region have implemented HBV0 due to logistical and contextual barriers and the lack of benefit when the mother is HBsAg-negative.[28,32]

[figure not shown]
The Health Ministry in Guinea-Bissau is planning to add HBV0 to the newborn vaccination program in 2028, in addition to the currently recommended BCG and OPV. Notably, since most African countries including Guinea-Bissau have no hepatitis B screening program, HBV0 is given to all neonates, even though it is only needed by those whose mothers are hepatitis B carriers. The majority of children are well protected against horizontal transmission by the three HepB vaccines included in the pentavalent vaccines provided at 6, 10 and 14 weeks of age. This makes it particularly important to ensure that there are no negative effects of HBV0.

HBV0 and non-specific effects

Hepatitis B vaccine was developed in 1982[27] and it has never been investigated whether HBV0 is associated with NSEs – beneficial or detrimental (**Figure 1**).

Figure 1. Effects on overall health of at-birth vaccines recommended by WHO.

Overall health effects in Guinea-Bissau of vaccines recommended at birth by WHO

This is a critical evidence gap for an effective and universally recommended intervention, particularly since two observational studies from West Africa have suggested that HepB vaccines provided later in infancy may be associated with negative NSEs.[33,34] In line with what has been seen for other non-live vaccines, this was particularly the case among females.[33,34]

HBV0 and atopic dermatitis

Several studies have found that delaying the first dose of aluminum-adjuvanted pentavalent vaccine is associated with a reduced risk of developing AD. In Australia, diphtheria-tetanus-pertussis (DTP) aluminum-adjuvanted vaccine is recommended at 2 months of age. In a study of 4,433 Australian children, receiving DTP with one month's delay was associated with reduced risk of eczema, aOR: 0.57 (0.34-0.97) and reduced use of eczema medication, aOR: 0.45 (0.24-0.83).[35] In a subsequent study of 143,429 Danish children, for whom DTP is recommended at 3 months of age, one month's delay was also associated with a reduced risk of eczema, aRR 0.94 (0.91-0.97), which was further reduced if the second dose was delayed as well, aRR=0.88 (0.82-0.93).[36]

In a recently published Danish study[37], it can be deduced that the incidence rate of AD among children who did not receive aluminum-containing vaccines was 0.6% (229/36,678), vs 0.9% (22,749/2,666,948) for those that had received an aluminum-containing vaccine. While not adjusted for confounders, this provides a crude relative risk of 0.73 (0.64-0.83) for those who did not get aluminum-containing vaccines vs. those who received aluminum-containing vaccines. Similar analyses point in the same direction for the combined group of atopic and allergic outcomes, the relative risk being 0.81 (0.75-0.89) ([Rapid response](#) to [37]).

HBV0 and neurodevelopment

Concerns have been raised regarding providing an aluminum-containing vaccine within 24 hours after birth.[38] Aluminum is known to be a neurotoxin.[39–41] This is particularly relevant in

infancy[42] and aluminum adjuvants have been speculated to be associated with neurodevelopmental disorders.[43,44] The recent Danish study[37] mentioned above found no association between the cumulative dose of aluminum received by age 2 years and subsequent development of neurodevelopmental disorders in 1,224,176 children, but Denmark does not use at-birth vaccines; the first dose of aluminum-containing pentavalent vaccine is provided at 3 months of age, so the study does not exclude an association between at-birth aluminum exposure and the risk of downstream neurodevelopmental disorders. This research question has to our knowledge never been addressed.

Previous studies and current plans for adding HBV0 to the at-birth schedule in Guinea-Bissau

In a small cross-sectional study utilizing blood samples from children aged 18 months, who were born before HBV vaccination was introduced in Guinea-Bissau in 2008 as part of the pentavalent vaccine series, 11% (21/187) were infected with Hepatitis B (HBsAg-positive) and 5% had recovered from infection.[45] A population-based study conducted by BHP between 2014-2016 reported a high (18.7%, 15% in women, 24% in men) prevalence of HBsAg among adults in urban Bissau[46], making vertical transmission a relevant public health concern which could be addressed by HBV0 vaccination. The Ministry of Health in Guinea-Bissau plans to introduce HBV0 for all newborns in 2028. There is therefore a **unique window of opportunity to conduct a large-scale RCT evaluating the overall health effects of HBV0** before vaccination becomes national policy. The proposed trial would address the significant knowledge gap regarding the overall health effects of HBV0.

2.2 Rationale for Current Study

The available evidence suggests that BCG and likely also OPV, especially given in combination, reduces all-cause neonatal mortality due to fewer cases of fatal sepsis and fewer respiratory infections.[1,2,4,15,23,24] Adding monovalent Hepatitis B vaccine would address the relevant public health threat of vertical Hepatitis B virus transmission, but the effect on overall health is unknown.

Concerns have been raised in relation to potential effects on the risk of unrelated infections (NSEs), atopic dermatitis and neurodevelopmental disorders. A randomized trial that compares the current neonatal vaccination schedule in Guinea-Bissau, BCG + OPV0, with the WHO-recommended schedule of BCG + OPV0 + HBV0 (**Figure 2**), is therefore needed to test whether healthy newborns given HBV0, co-administered with BCG + OPV0, modulates the risk of these outcomes, which needs to be counterbalanced against the well-known benefits of HBV0.

Figure 2. The current vaccination schedule in Guinea-Bissau up to 14 weeks of age (control, top) and the WHO-recommended vaccine schedule (intervention, bottom)

	Birth	6 weeks of age	10 weeks of age	14 weeks of age
Control group: Current vaccination schedule in Guinea-Bissau	BCG OPV0	ROTA-1 DTP-HepB-Hib1 PCV13-1 OPV1	ROTA-2 DTP-HepB-Hib2 PCV13-2 OPV2	IPV DTP-HepB-Hib3 PCV13-3 OPV3
Intervention group: Vaccination schedule recommended by WHO (HBV0 at birth added)	HBV0 BCG OPV0	ROTA-1 DTP-HepB-Hib1 PCV13-1 OPV1	ROTA-2 DTP-HepB-Hib2 PCV13-2 OPV2	IPV DTP-HepB-Hib3 PCV13-3 OPV3

Abbreviations: BCG, Bacille Calmette-Gérin; OPV, Oral Polio Vaccine; HBV0, Hepatitis B vaccine at birth; HepB, Hepatitis B vaccine in infancy; ROTA, Rotavirus vaccine; DTP, Diphtheria-Tetanus-Pertussis; Hib, Hemophilus Influenzae; PCV, Pneumococcus vaccine; IPV, Inactivated Polio Vaccine.

2.3 Research Questions

Does the administration of a single dose of neonatal monovalent HBV0 to newborns within 1 week of age reduce or increase all-cause mortality and non-fatal admission with infection (composite outcome) in the first 42 days of life?

Does the administration of a single dose of neonatal monovalent HBV0 to newborns within 1 week of age affect the risk of AD by 2 years of age?

Does the administration of a single dose of neonatal monovalent HBV0 to newborns within 1 week of age affect neurocognitive outcomes by 5 years of age?

Are there sex-differential non-specific effects of HBV0?

3. STUDY OBJECTIVES

3.1 Primary Objective

We will investigate whether the administration of a single vaccine dose of pediatric monovalent HBV0 provided within 1 week of birth is associated with the composite outcome of all-cause mortality and severe morbidity (non-fatal hospital admission with infection) within 42 days after birth (the age when the next routine vaccines are given).

3.2 Secondary Objectives

To investigate the effect of HBV0 on AD by 2 years of age.

To investigate the effect of HBV0 on neurodevelopment by 5 years of age.

For all outcomes, it will be assessed whether there are sex-differential effects of HBV0.

4. STUDY DESIGN

4.1 Type of Study

The study will be a single-blind, multi-center, phase IV randomized controlled trial enrolling healthy neonates that are ≤ 1 week of age. The main recruitment center will be the Maternity Ward of Hospital Nacional Simão Mendes (HNSM), which has approximately 8,000 births/year. The HNSM Director approved to host the trial on September 12, 2025. The trial will begin at HNSM (**Phase I**), and then expand to additional recruitment units, pending approval from each health facility:

Phase II:

Bandim Health Center (~200 births per year).

Hospital de Cumura (~700 births per year).

Hospital Militar (~1,000 births per year).

All inclusion sites are located in the greater Bissau area of Guinea-Bissau. We aim to recruit at least 14,500 children (see sample size calculation) during a 2-year period. Eligible newborns will be randomized 1:1 to receive a neonatal dose of monovalent HBV0 co-administered with BCG + OPV0 vs only BCG + OPV0.

Trial design and participant recruitment: Eligibility screening will occur at discharge from the birth facility, or at the health facility when a newborn born elsewhere comes for vaccination. If the mother is a known Hepatitis B carrier, the child will be excluded and offered Hepatitis B vaccine. Newborns are eligible if they are clinically stable and unvaccinated. Moribund neonates and children with major malformations will be excluded. Informed written consent will be obtained from mothers/guardians following an oral explanation in Portuguese Creole and a written trial explanation in Portuguese. Participation is voluntary, and families may withdraw from the trial at any time. Baseline information such as maternal and neonate mid-upper-arm circumference, maternal BCG scar status, socio-economic factors and phone contacts for the mother, the father and family members will be collected, as done previously.[3,5,6]

Randomization and blinding: Randomization will be performed using sealed envelopes prepared in blocks of 24, stratified by sex and place of inclusion. After the informed consent procedure, the mother/guardian selects a sealed envelope allocating the neonate to either the intervention group (HBV0) or the control group. The mother/guardian and the inclusion team will not be blinded to group allocation. All outcome assessors involved in follow-up procedures and the trial statistician will be blinded, ensuring objective outcome assessment while maintaining operational feasibility.

Intervention: All enrolled neonates will receive BCG (0.05 mL intradermal injection in the left deltoid) and OPV0 (2 oral drops), in accordance with national guidelines. The intervention group will additionally receive 0.5 mL of monovalent HBV0 intramuscularly in the anterolateral aspect of the thigh, with no placebo used in the control group. BCG and OPV are currently provided to all newborns at HNSM on weekdays, aside from situations with national vaccine stockout, which are rare. At the smaller hospitals and health centers, OPV is provided daily on weekdays while BCG is typically available on one vaccination day during the week, to reduce vaccine wastage. The trial team will ensure that the necessary vaccines (BCG, OPV, HBV0) are available on all days of the week (including holidays and weekends) at HNSM and on normal workdays (excluding holidays and weekends) at the smaller inclusion sites.

4.2 Follow-up Measures

To ensure comprehensive outcome data, follow-up of all children will be conducted through 5 complementary mechanisms, including telephone interviews (**A**), home visits (**B**), hospital surveillance (**C**), investigation of AD incidence up to 2 years of age (**A**, **B**, **D**), and a neurodevelopmental assessment by 5 years of age (**E**).

A) Telephone interviews at age 1 week, 6 weeks, 6 months, 1 year and 2 years of age.

Families will be contacted to assess vital status, hospital admissions, adherence to the recommended routine vaccination schedule (at 6, 10 and 14 weeks), and morbidity. If an infant has died, brief information will be collected regarding the circumstances such as date, location (home or hospital), and symptoms. In prior BHP trials, 99% of families provided at least 1 telephone contact, and >95% successfully provided data on vital status by 6 weeks of age (**Table 1**).[5]

Table 1. BCGSTRAIN II[5] Telephone follow-up data.

Mother supplied telephone number(s) at inclusion	99%
Follow-up success rate (combined for 6-week and 6-month calls)	95%
Successful 6-week follow-up if two phone numbers provided	88%
Successful 6-week follow-up with ≥ three phone numbers provided	97%

This demonstrates the feasibility and minimal loss to follow-up with telephone-based interviews in our setting. Each reported death will be sought separately confirmed by two different follow-up sources (e.g., two separate telephone contacts or one telephone contact and hospital admission outcome data).

B) Cohort of BHP HDSS study area infants: home visit by 2 months and 12 months of age

Approximately 15% (~2,100 with 14,500 inclusions) of the newborns will reside in BHP's Health and Demographic Surveillance System (HDSS) study area. These infants will receive a home visit at 2 and 12 months of age to assess vital status, BCG scar status and morbidity incidence, as done in previous trials.[1,3–5] In addition, the families will be asked about previous symptoms of AD and the infant will be examined for signs of AD. In case AD is suspected, the child will be referred to an AD specialist (see below). For HDSS infants that die, a verbal autopsy will be performed 3-6 months after the death.

C) Hospital admission surveillance

All admissions to the national hospital's pediatric ward HNSM are monitored and entered daily by a dedicated BHP team.[2,3,47,48] Parental names and telephone numbers are registered for all admissions and will be used for data linkage and data confirmation. Admission charts linked via a unique trial participant vaccination card sticker ID include the diagnosis and admission outcome. For approximately 60% of admitted infants, data from the vaccination card including the unique ID is documented during the admission. To identify remaining admissions not registered with the unique trial ID, a previously validated standardized probabilistic record matching protocol will be applied.[2,3,5] All admissions will be manually vetted by a blinded senior researcher. To assess the likely cause of death or admission, we will use both hospital data, telephone follow-up data, and verbal autopsy data from the BHP study area.

D) Assessment of AD

At the telephone contacts and HDSS home visits, we will ask the mother whether the child has an itchy rash. If the caregiver reports that the child has scratched repeatedly and/or experienced sleep disturbances due to itching and the family resides in the greater metropolitan area of Bissau, a home visit will be offered by a physician experienced in diagnosing AD at a time point where the child suffers from the rash.

At the home visit, the physician will perform a clinical examination to assess whether the child has AD or another condition. Appropriate treatment will be initiated, and guidance will be given for clinical follow-up. At follow-up visits, it will be ascertained if the treatment has helped, and/or if further/other treatment is needed. The data on 1) self-reported AD symptoms and 2) physician-diagnosed AD will be reported separately for the AD outcome.

E) Neurodevelopmental assessment

A subgroup of 500 BHP HDSS children will receive a neurodevelopmental assessment at 5 years of age, provided renewed informed consent. The evaluation will take place at the local health center.

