4.3 Primary and Secondary Outcome Measures

Primary outcome: Mortality and morbidity

The composite outcome of all-cause mortality or first non-fatal admission with infection from randomization to 42 days of age (before the next routine vaccination) in the group given HBV0 compared with the control group.

Secondary outcomes: Neurodevelopmental disorders and AD

AD by 2 years of age

In a subgroup followed to 2 years of age (see sample size calculation): cumulative incidence of AD symptoms (self-reported at home visits or telephone follow-up) and cumulative incidence of AD diagnosed by an MD with special training.

Neurodevelopment by 5 years of age

In a subgroup of 500 singleton children from the HDSS followed to 5 years of age: cognitive outcomes assessed by the Mullen Scales of Early Learning and the Kaufman Assessment Battery for Children. These tests have been tested for validity in Sub-Saharan African children.[49–52]

The outcomes will be further explored to assess the effect by subcategory of outcome and by age (**Table 2**).

Table 2. Trial outcomes and data sources

Primary outcome	Whom	Age assessed	Data source(s)
Composite outcome: all-cause mortality and admission due to non-fatal infection	All infants	6 weeks	A, B, C
Secondary outcomes			
I: Self-reported AD and II: physician-diagnosed AD	I: All infants. II: To 200 cases among controls*	2 years	A, B, D
Neurodevelopmental outcomes	500 HDSS children*	5 years	E
Outcome subcategories and by age			
Composite outcome: all-cause mortality and admission due to non-fatal infection	All infants	2 years	A, B, C
All-cause mortality	All infants	6 weeks, 2 years	A, B, C
In-hospital case-fatality (all-cause, infectious diseases)	Hospitalized infants	6 weeks, 2 years	C
Hospital admission for major diseases groups (neonatal conditions aside from sepsis, respiratory infections, bronchitis, diarrheal diseases, malaria, malnutrition-related diseases)	All infants	6 weeks, 2 years	C

* See sample size calculation section below for further information.

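### As worded, the telephone question on atopic dermatitis has no look-back, so it would capture the stated cumulative incidence by 2 years only incompletely

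*Protocol*

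**What the plan says.** **Outcome.** Protocol section 4.3 defines the self-reported AD outcome as "cumulative incidence of AD symptoms (self-reported at home visits or telephone follow-up"), to 2 years of age. Table 2 assigns it to all infants. Section 4.4 supposes a 10% cumulative incidence by 2 years, which is 725 control cases with 7,250 per arm. Section 8.2 analyses cumulative incidence by binomial regression.

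**Question and timing.** Section 4.2 D states: "At the telephone contacts and HDSS home visits, we will ask the mother whether the child has an itchy rash". Section 4.2 A sets the schedule: "Telephone interviews at age 1 week, 6 weeks, 6 months, 1 year and 2 years of age". It describes the content of the calls in general terms: "Families will be contacted to assess vital status, hospital admissions, adherence to the recommended routine vaccination schedule (at 6, 10 and 14 weeks), and morbidity".

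**Home visits.** Section 4.2 B says: "Approximately 15% (~2,100 with 14,500 inclusions) of the newborns will reside in BHP's Health and Demographic Surveillance System (HDSS) study area". These infants are visited at 2 and 12 months, when "the families will be asked about previous symptoms of AD and the infant will be examined for signs of AD".

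**Step to the physician.** The trigger in section 4.2 D is limited to families living in and around the capital. It begins: "If the caregiver reports that the child has scratched repeatedly and/or experienced sleep disturbances due to itching and the family resides in the greater metropolitan". When this condition is met, the plan is that "a home visit will be offered by a physician experienced in diagnosing AD at a time point where the child suffers from the rash".

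**The concern.** The outcome counts every child who has had AD symptoms by age 2. The only AD question given for telephone contacts is in the present tense. The protocol itself treats the rash as intermittent, because it times the physician's visit to an episode. If interviewers follow the text as written, a child whose rash starts and clears between two calls is recorded as never affected. The longest gap is the whole second year, which rests on the 2-year call alone.

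The look-back is stated for HDSS home visits and for no telephone contact. One outcome is therefore ascertained in two ways.

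At stake are the absolute risk the trial will report, the number of self-reported cases, and the number of children who must be followed to reach 200 physician-diagnosed control cases. Episodes not asked about at the time cannot be reliably recovered later.

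**Working it through.** **1. Who is affected, and when.**
- HDSS share: 2,100 / 14,500 = 14.5%, so 85.5% (12,400 infants) have telephone contacts only.
- Outside the HDSS, no look-back is stated at any age.
- Inside the HDSS, the look-back covers the period up to the 12-month visit. From 12 to 24 months these children depend on the same 2-year call as everyone else.

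**2. The plan's own AD figures.** Expected control cases: 7,250 × 0.10 = 725. The 200-case target corresponds to 200 / 0.10 = 2,000 children per arm. Section 4.4 states neither alpha nor power for AD; I take two-sided 0.05 and 80% from the primary outcome. Power for two proportions is

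Φ{(|p1 − p2| − 1.96·√[2·p̄(1 − p̄)/n]) / √[p1(1 − p1)/n + p2(1 − p2)/n]}, where p̄ is the mean of p1 and p2.

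- n = 2,000, 10% vs 12.8% (200 vs 256 cases): 79.6%.
- n = 2,000, 10% vs 7.5% (200 vs 150 cases): 79.9%.

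The plan's figures reproduce.

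**3. What repeated current-status questions capture.** Suppose an affected child has a rash at any one contact with probability q, independently across contacts. Both are assumptions; the documents give no q. The share of affected children detected over k informative contacts is 1 − (1 − q)^k:

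| q | k = 1 | k = 2 | k = 3 | k = 5 |
|---|---|---|---|---|
| 0.2 | 20% | 36% | 49% | 67% |
| 0.4 | 40% | 64% | 78% | 92% |
| 0.6 | 60% | 84% | 94% | 99% |

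Onset after 1 year leaves k = 1. Onset between 6 months and 1 year leaves k = 2. The measure is a positive report at one or more contacts, and how complete it is depends on age at onset.

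**4. Effect on case counts and power.** Let s be the overall share of true cases captured, equal in both arms. Observed risks are s·p0 and s·p1, so with few false positives the observed ratio is (s·p1)/(s·p0) = p1/p0. Self-reported AD is evaluated at n = 7,250 per arm with a true control risk of 10%. Controls needed for 200 cases = 200 / (0.10·s).

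| s | Self-reported control cases | Power, RR 1.28 | Power, RR 0.75 | Controls needed for 200 cases |
|---|---|---|---|---|
| 1 | 725 | >99% | >99% | 2,000 |
| 0.75 | 544 | 99.5% | 99.5% | 2,667 |
| 0.5 | 363 | 95.3% | 95.7% | 4,000 |
| 0.25 | 181 | 71.7% | 73.0% | 8,000 |

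The last column assumes that every captured case is visited and confirmed. The 8,000 exceeds the 7,250 planned per arm, though it lies within the ceiling of 12,500 per arm in section 6.8. The 200-case target becomes unreachable at 7,250 per arm only when s falls below 200 / 725 = 28%.

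**The case against.** The strongest reply is that the point rests on the tense of one verb in a prose summary.

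- The same sentence covers HDSS visits, where a look-back is known to be asked, so its wording need not exclude one by telephone.
- The next sentence acts on whether the child has scratched repeatedly or slept badly, which is history wording and applies to both kinds of contact.
- The physician's visit may follow the call, so a report made between flares is foreseen.
- Calls also cover morbidity in general.
- The follow-up questionnaire is not appended (only the inclusion form is) and may contain a recall item.

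This stands to the extent that the text is ambiguous. A reader might infer that the trial asks only about a current rash; the documents do not establish that. But the history wording sets the trigger for a physician visit. It gives no recall period and does not say that a resolved episode counts as a self-reported case. Morbidity is too general a term to supply one.

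It is also fair that the consequences for the comparison are limited. Allocation is randomized and stratified by place of inclusion, self-reported AD keeps about 95% power at 50% capture, and the physician-diagnosed part is driven by a case target. HDSS residence is not among the effect modifiers in section 8.3, so the difference in ascertainment harms no listed subgroup analysis. It still mixes two measures in one reported risk.

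**Conclusion.** The point holds as a mismatch between the stated outcome and the stated question. Followed literally, section 4.2 D yields an incompletely ascertained cumulative incidence, measured differently inside and outside the HDSS during the first year and with a 12-month gap for all infants in the second.

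The direction is clear: an understated absolute risk, fewer than the assumed 725 self-reported control cases, and more children needed for 200 diagnosed control cases. The size is not. The tables rest on assumed values of q and s, on independence between contacts, and on the plan's own 10% risk.

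Three stronger readings are not supported:
- That the trial would measure point prevalence. Reports accumulate over five calls, which gives an incomplete cumulative proportion.
- That the gap is confined to infants outside the HDSS. Home visits stop at 12 months.
- That the risk ratio is biased. Equal under-capture leaves it roughly unchanged, and nothing in this point shows a difference in capture between arms.

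This is a cheap and worthwhile improvement to a secondary outcome, best settled before calls are made.

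**What to change.** Reconcile sections 4.2 B, 4.2 D and 4.3. State in 4.2 D that every telephone contact asks two things: whether the child has had an itchy rash at any time since the last contact, and whether it is present now. State that a yes to either counts as a self-reported case. If the follow-up form already asks this, correct the protocol text to match.

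If the look-back is not wanted, describe the outcome in 4.3, 4.4 and 8.2 as AD symptoms reported at scheduled contacts, and do not call it cumulative incidence by 2 years.

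The cost is one reworded question and one short added item, with no extra contact. The downside is some recall error over the intervals of 6 to 12 months. Recording whether the rash is present now lets the analysts compare recalled with current reports and examine that error.
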